4.1. Study Endpoints

Statistical analysis and/or summarization is planned for the following study endpoints. Complete details on how endpoints are calculated and compared across treatment arms are presented in the subsections below. A key to abbreviated terms appears in Section 2.

Table 1. Study Endpoints

Primary Efficacy Endpoint

 CR Rate: percentage of patients who achieve a CR as assessed by the investigator following treatment with alvocidib

Secondary Efficacy Endpoints (not listed in order of importance)

- CR_{MRD}
 Rate: percentage of patients who achieve a CR and test negative for minimal residual disease (MRD) using standardized techniques such as multiparametric flow cytometry or next generation sequencing
- Combined CR Rate: percentage of patients achieving a combined CR (CR or CRi) following treatment with alvocidib
- Combined Remission Rate: percentage of patients achieving a combined remission (CR, CRi or PR) following treatment with alvocidib
- Overall Survival: time from the date of first dose (Day 1) until death from any cause
- Progression-Free Survival: time from the date of first dose (Day 1) until (a) treatment failure, (b) relapse after combined remission (CR, CRi or PR), or (c) death from any cause, whichever occurs first
- Relapse-Free Survival Following CR (defined only for patients who achieve a CR during the study): time from the date of CR (Day 1) until (a) relapse after CR, or (b) death from any cause, whichever occurs first

Table 1. Study Endpoints

- Relapse-Free Survival Following Combined CR (defined only for patients who achieve a combined CR during the study): time from the earliest date of combined CR (Day 1) until (a) relapse after combined CR, or (b) death from any cause, whichever occurs first
- Relapse-Free Survival Following Combined Remission (defined only for patients who achieve a combined remission during the study): time from the earliest date of combined remission (Day 1) until (a) relapse after combined remission, or (b) death from any cause, whichever occurs first
- CR Duration (defined only for patients who achieve a CR during the study):
 time from the date of CR (Day 1) until relapse after CR
- Combined CR Duration (defined only for patients who achieve a combined CR during the study): time from the earliest date of combined CR (Day 1) until relapse after combined CR
- Combined Remission Duration (defined only for patients who achieve a combined remission during the study): time from the earliest date of combined remission (Day 1) until relapse after combined remission
- Stem Cell Transplant Rate: percentage of patients proceeding directly to stem cell transplantation within 90 days after their last dose of study drug

Safety Endpoints (not listed in order of importance)

- 30- and 60-Day Mortality
- Adverse Event Incidence Rates
- Time to neutrophil recovery ≥1x10⁹/L
- Time to platelet recovery ≥100x10⁹/L
- Presence and Severity of Tumor Lysis Syndrome
- Clinical Laboratory Parameters
- Vital Signs

Other Endpoints

Concomitant Medication Usage Rates

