5.5 End of Study Assessments

If, at any time, a patient discontinues study treatment, a visit should be scheduled as soon as possible and within 14 days of the last dose of study drug or within 14 days of the decision to discontinue study treatment. If the decision to withdraw the patient occurs at a regularly scheduled visit, that visit may become the End of Study visit rather than having the patient return for an additional visit.

- Complete physical examination including weight (kg) and other measures of disease and disease symptoms, eg, extramedullary disease
- Vital signs (temperature, heart rate, systolic and diastolic blood pressures)
- ECOG PS (*Appendix B*)
- Collect blood for evaluation of laboratory studies (*Appendix D*):
 - Hematology
 - Full serum chemistry panel (as clinically indicated)
 - Fibrinogen level (only required if clinically indicated)
- Urinalysis
- Perform bone marrow biopsy and/or aspiration (if not done in the preceding 30 days) for determination of disease status including MRD and assessment of other potential biomarkers. If the bone marrow biopsy and/or aspirate is nonproductive or not diagnostic, the procedure must be repeated within 7-10 days.
- Perform 12-lead ECG (as clinically indicated)
- Perform ECHO or MUGA scan (as clinically indicated)
- Assess for AEs
- Record only those medications (prescription, nonprescription, nutritional supplements) administered in conjunction with an AE

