5.6 Follow-up Assessments

5.6.1 Safety Follow-up (30 Days Post Last Dose)

Patients must have a safety evaluation 30 days after the last dose of study drug. The following assessments will be performed:

- Assess for AEs
 - Ongoing AEs must be followed clinically until the event is resolved, deemed stable, or the patient starts another treatment for their disease
- Record only those medications (prescription, nonprescription, and nutritional supplements) administered in conjunction with an AE, as well

as any antineoplastic therapies initiated since discontinuation of study drug.

5.6.2 Long-term Follow-up (Starting 30 Days Post End of Study out to 2 Years)

Additionally, all study patients will be attempted to be contacted by phone, if possible, every 6 months to assess for date of death, date of stem cell transplant, date of relapse, or continued remission beginning the month after the patient completes the End of Study assessments to 24 months after Day of First Dose regardless of how many cycles a patient receives. When telephone contact is not possible, medical records will serve as the surrogate to assess for these outcomes.

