Cycle 1: period of time from the first dose of study drug until the start of study drug in cycle 2 or the start of alternative AML therapy other than supportive measures such as blood product transfusions (hence a patient whose first response assessment in cycle 1 is a CRi is considered to have achieved CR if neutrophils and platelets recover prior to initiation of cycle 2 or alternative AML therapy)

Combined CR Rate: percentage of patients who achieve a combined CR following treatment with alvocidib

Combined Remission Rate: percentage of patients who achieve a combined remission following treatment with alvocidib

CR Rate: percentage of patients who achieve a CR following treatment with alvocidib (see section 7.8.1)

Dose-Limiting Toxicity: Refer to the study protocol for the specific conditions and events that qualify as a dose-limiting toxicity (DLT)

Intent-to-Treat Population: all patients enrolled in the study regardless of whether they actually received study drug and regardless of whether evidence is found indicating they failed to meet study inclusion/exclusion criteria or had other protocol violations (see section 7.1)

Minimal Residual Disease Negative: Absence of gene fusion transcripts using standardized techniques such as multiparametric flow cytometry or next generation sequencing

Neutrophil Recovery: Absolute neutrophil count ≥1x10⁹/L following the administration of study drug

Per-Protocol Population: The subset of safety patients who either (a) have at least one response assessment on study, or (b) die prior to their first scheduled response assessment; however, patients are excluded from the per-protocol population if they have an important protocol deviation, such as when evidence is found indicating they failed to meet any study inclusion/exclusion criterion (see section 7.1)

Platelet Recovery: Platelet count ≥100x10⁹/L following the administration of study drug

Prestudy: Occurrence prior to the first administration of study drug

Safety Population: The subset of intent-to-treat patients who received at least one dose or partial dose of study drug (see section 7.1)

Shift Table: two-way frequency table pairing baseline value with the most extreme post-baseline result

Study Drug: alvocidib, Ara-C (cytarabine) and mitoxantrone

Treatment Failure: failing to achieve a CR, CRi or PR following induction therapy (see section 7.8.2)

4. Introduction

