7.8.2. Progression-Free Survival

PFS time is defined for all patients and is measured from the date of first dose (Day 1) until (a) treatment failure, (b) relapse after combined remission, or (c) death from any cause, whichever occurs first.

Treatment failure is defined as failing to achieve a combined remission following induction therapy. The date of treatment failure is defined by the earliest bone marrow collection following the first induction attempt regardless of whether the patient received a second induction attempt (unless the second induction resulted in a combined remission in which case "treatment failure" does not apply).

Additional rules for defining PFS time are:

- A patient found to have relapsed after missing one or more scheduled response assessments will have his PFS time end on the scheduled date for the first missed response assessment following the last confirmation of combined remission
- A patient who misses the first scheduled response assessment and who never achieves combined remission will have his PFS time end on the scheduled date for the first response assessment (unless the patient died before this date)

Patients enrolled subsequent to protocol amendment 6 were scheduled to be followed for 2 years following the end-of-study visit, whereas patients enrolled prior to protocol amendment 6 were followed for only 30 days following the end-of-study visit unless they reconsented to the amendment-6, 2-year follow-up period. The definition of PFS time and the following rules for censoring PFS time apply to all patients regardless of follow-up duration.

Rules for censoring PFS time are:

- A patient with PFS continuing as of the date he is lost to follow-up will have his PFS time censored on the date of his last response assessment
- A patient with PFS continuing as of the database lock will have his PFS time censored on the date of his last response assessment

Summary statistics will include the number and percentage of censored PFS times, quartile PFS times, 95% CIs for the quartile PFS times, and KM "survival" percentages¹⁰ with 95% CIs at select milestone times (e.g., 6, 12 and 18 months).

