7.8.3. Overall Survival

OS time is defined for all patients and is measured from the date of first dose (Day 1) until death from any cause. Patients enrolled subsequent to protocol amendment 6 were scheduled to be followed for 2 years following the end-of-study visit, whereas patients enrolled prior to protocol amendment 6 were followed for only 30 days following the end-of-study visit unless they reconsented to the amendment-6, 2-year follow-up period. The definition of OS time and the following rules for censoring OS time apply to all patients regardless of follow-up duration.

Rules for censoring OS time are:

- A patient with OS continuing as of the date he is lost to follow-up will have his OS time censored on the date of his last assessment of any type
- A patient with OS continuing as of the database lock will have his OS time censored on the date of his last assessment of any type

Summary statistics will include the number and percentage of censored OS times, quartile OS times, 95% CIs for the quartile OS times, and KM survival percentages with 95% CIs at select milestone times (e.g., 6, 12 and 18 months).

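### The stem cell transplant rate looks 90 days past the last dose, but follow-up of some patients can end sooner and the SAP has no rule for their unknown status

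*SAP*

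**What the plan says.** SAP section 4.1 (Table 1) lists the stem cell transplant rate among the secondary efficacy endpoints: the "percentage of patients proceeding directly to stem cell transplantation within 90 days after their last dose of study drug". SAP section 9 (Table 3) tabulates it for the ITT and per-protocol populations, and section 7.1 puts every enrolled patient in the ITT population.

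On follow-up, SAP 7.8.3 states that "patients enrolled prior to protocol amendment 6 were followed for only 30 days following the end-of-study visit unless they reconsented" to the two-year follow-up. The same caveat stands in 7.8.2, 7.8.4 and 7.8.5. Protocol 5.5 sets the End of Study visit "within 14 days of the last dose of study drug or within 14 days of the decision to discontinue study treatment".

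In the current protocol, 5.6.1 requires a safety evaluation 30 days after the last dose. Section 5.6.2 then has all study patients contacted "every 6 months to assess for date of death, date of stem cell transplant, date of relapse, or continued remission", and adds: "When telephone contact is not possible, medical records will serve as the surrogate to assess for these outcomes".

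SAP section 3 defines study drug as "alvocidib, Ara-C (cytarabine) and mitoxantrone". Protocol 9.1 describes alvocidib as the investigational study drug.

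**The concern.** A percentage over a fixed window is sound only if each patient is observed to the end of the window or has an outcome that settles the matter earlier. Here the window is 90 days, and for some patients the follow-up that the SAP describes can be shorter.

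The SAP handles short follow-up elsewhere. PFS, OS, relapse-free survival and CR duration each have censoring rules. The transplant rate has none. Section 4.1 promises full details of how endpoints are calculated, but section 7.8 has no subsection for this one. The missing-value rules in 7.2 cover absent bone marrow and time-to-event endpoints only.

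If a patient whose observation ended early stays in the denominator and has no recorded transplant, the rate is too low by an amount that the table would not show.

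**Working it through.** **The plan's own figure.** The only transplant figure in either document is in the SAP Appendix 2 sample table (patient disposition): 3 of 22 with a post-study transplant. 3/22 = 13.6%, as printed. This is a template row for post-study transplant, not the 90-day endpoint, so it serves only as illustration.

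**Who could be affected.** The same template places 1 + 8 + 13 = 22 of 22 patients under Amendments 2 to 4, all before Amendment 6.

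**Days observed after the last dose**, for a pre-Amendment-6 patient who did not reconsent:

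days observed = (day of End of Study visit − day of last dose) + 30; shortfall = 90 − days observed, or zero if negative.

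| Case | Days observed | Shortfall |
|---|---|---|
| Visit 14 days after last dose | 14 + 30 = 44 | 46 (46/90 = 51%) |
| Induction only, last cytarabine Day 11, decision and visit on Day 50 | 50 − 11 + 30 = 69 | 21 |
| Same, visit 14 days after a Day 50 decision | 64 − 11 + 30 = 83 | 7 |
| Same, visit 14 days after a Day 53 decision | 67 − 11 + 30 = 86 | 4 (4/90 = 4%) |
| Visit 60 or more days after last dose | at least 90 | none |

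The 44-day case is the latest visit that counting from the last dose allows; an earlier visit gives fewer days. A visit at 60 days or more is possible because the decision to discontinue can come late: protocol 4.1 lets consolidation start up to 90 days after recovery.

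**Which drug starts the clock.** The induction rows count from cytarabine on Day 11. If only alvocidib counts, the last dose of a single induction is on Day 3, and the Day 53 case gives 97 − 3 = 94 days, so no shortfall. The Day 50 same-day case would still give 50 − 3 + 30 = 77. If cytarabine counts, consolidation with high-dose cytarabine restarts the 90 days.

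**How classification could matter.** In the template's 30/60 mg/m² column all 13 patients are shown as not transplanted, there is no row for unknown, and 8 of the 13 have a missing withdrawal reason. The printed overall mean of 13.6 weeks on study suggests that those 8 have no exit date:

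- all 22: (3×19.7 + 3×15.0 + 3×15.0 + 13×8.1)/22 = 11.6
- without the 8: (3×19.7 + 3×15.0 + 3×15.0 + 5×8.1)/14 = 13.5, or 13.49 to 13.59 allowing for rounding of the inputs

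Treating those 8 as unknown gives these illustrative rates with exact 95% intervals:

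- unknown counted as no: 3/22 = 13.6% (2.9 to 34.9)
- known only: 3/14 = 21.4% (4.7 to 50.8)
- unknown counted as yes: 11/22 = 50.0% (28.2 to 71.8)

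These are bounds on template counts, not trial results.

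**The case against.** Four points on the other side have weight.

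- **The transplants may be observed after all.** Reconsented patients have the date collected. Protocol 5.6.2 speaks of all study patients and allows medical records as back-up, and the template has a post-study transplant row for patients from Amendments 2 to 4. This stands as far as it goes: loss is a risk, not a certainty. But it conflicts with the SAP's statement that some patients were followed for only 30 days, and the two must be reconciled.
- **The gap may be small.** The template's 30/60 mg/m² column, where 9 of 13 had no consolidation cycle, has a median of 9.0 weeks on study, about Day 63. If that is the End of Study visit and Day 11 the last dose, 63 + 30 − 11 = 82 of 90 days are observed. This also stands, and the 44-day case should not be read as typical.
- **A reader might infer that unobserved patients are counted as not transplanted.** The SAP does not say so. Its only rule that treats missing as failure concerns bone marrow and remission. The reading is plausible from the ITT denominator and the Yes/No rows of the template, but a template is not a rule.
- **A reader might also infer a false rise in transplant rate with dose**, since lower doses enrolled first. The documents do not support it. In the template all four dose levels precede Amendment 6 and share the same follow-up rule, and its transplants run the other way (1 of 3 at each lower dose level, 0 of 13 at the highest). Unequal reconsent could separate the dose levels, but no figures are given.

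The endpoint's standing also limits the point: it is not among the protocol's listed efficacy evaluations, and protocol 7.2 says a formal efficacy analysis is not appropriate.

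**Conclusion.** The point holds in a limited form. For patients enrolled before Amendment 6 who did not reconsent, observation can end before day 90 after the last dose, and the SAP has no censoring or unknown-status rule for the transplant rate. A simple percentage with all patients in the denominator can therefore understate it.

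The shortfall is 46 of 90 days if the End of Study visit is 14 days after the last dose, 4 of 90 in the late-decision case counted from Day 11, and nothing if the decision is later or, in that late case, if only alvocidib starts the clock. A reader might take 51% as the share of transplants missed. That would require transplants spread evenly over the 90 days, for which the documents give no basis; the endpoint counts patients who go directly to transplant.

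The size of any bias cannot be computed, because neither the number who reconsented nor the timing of transplants is given. No dose-related direction can be claimed. The endpoint is descriptive and drives no dose decision, so the severity is minor to moderate.

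**What to change.** 1. Reconcile the SAP's follow-up statement with protocol 5.6.2, and use telephone contact or medical records to establish transplant status at day 90 where consent allows.
2. State in SAP Table 1 which drug's last dose starts the 90 days, and bring the SAP definition of study drug into line with the protocol.
3. In the transplant table, report the number observed to day 90 and the number with unknown status. Show the rate with unknowns counted as no beside the rate among patients whose status is known.
4. For all dose levels pooled, add a 90-day cumulative incidence of transplant from the last dose, censored at last contact, with death as a competing event. Decide how relapse before transplant is handled, and apply the same choice in the table and in the estimate. Cohorts of 3 to 6 are too small for this estimate by dose level.

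The cost is some SAP wording, two extra counts, one pooled estimate and the record checks in item 1. The downside is a wider interval and a visible count of patients with unknown status.

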4.2. Statistical Objectives

The statistical objectives are threefold:

- 1. To define a maximum tolerated dose of alvocidib administered with cytarabine and daunorubicin in newly diagnosed AML patients
- 2. To describe the safety and efficacy of alvocidib administered with cytarabine and daunorubicin in newly diagnosed AML patients

3. To model the relationship between baseline MCL-1 dependence and response to treatment with alvocidib administered with cytarabine and daunorubicin

5. Sample Size

The sample size for this study is not predetermined. The number of patients enrolled depends on the occurrence and pattern of DLTs.

6. Treatment Assignment

Cohorts of 3 patients are assigned a dose of alvocidib according to standard 3+3 dose escalation/de-escalation rules. All patients receive the same, standard doses of cytarabine and daunorubicin.

7. Statistical Methods

Analyses will be performed using SAS statistical software. Default estimation methods in version 9.4 of SAS are always used unless an alternative is specified below. Data summaries will include the mean, standard deviation, median, minimum and maximum values for continuous data; the median, 25th and 75th percentiles, minimum and maximum values for time-to-event endpoints; and the number and percentage of patients in each category for categorical data. Pointwise 95% confidence intervals (CI) will also be estimated for the mean (continuous data), median (time-to-event endpoints) or percentage of patients (categorical data).

In general, data values will be obtained directly from the clinical database (e.g., birth date, treatment dates, AML relapse date and death date). Derivations for certain values not collected explicitly in the database are explained in relevant sections below (e.g., age and treatment failure date, sections 7.6 and 7.8.2, respectively). In some instances, it is beyond the scope of this SAP to explain schemes for patient classifications and data derivations (e.g., classifying patients in cytogenetic risk group according to published criteria). These details will be expounded in the clinical study report.

Durations of time expressed in months (e.g., times-to-event endpoints) will be reported in proportional "months" according to the formula

months =
$$\frac{12}{365.25} \times \text{days}$$

Baseline value of a characteristic is defined as the last measured value prior to the first dose of study drug.

7.1. Analysis Populations

The intent-to-treat (ITT) patient population includes all patients enrolled in the study regardless of whether they actually received study drug and regardless of whether evidence is found indicating they failed to meet study inclusion/exclusion criteria or had other protocol violations. When the ITT patient population is analyzed, patients are grouped according to their assigned alvocidib dose regardless of actual dose received. The ITT patient population is the analysis population for the primary analyses of efficacy endpoints.

The safety patient population is the subset of ITT patients who received at least one dose of study drug. When the safety patient population is analyzed, patients are grouped according to the actual alvocidib dose received. The safety patient population is the analysis population for all analyses of safety data.

The per-protocol patient population is the subset of safety patients who either (a) have at least one response assessment on study, or (b) die prior to their first scheduled response assessment. However, patients are excluded from the per-protocol patient population if they have an important protocol deviation, such as when evidence is found indicating they failed to meet any study inclusion/exclusion criterion. When the per-protocol patient population is analyzed, patients are grouped according to their assigned alvocidib dose regardless of actual dose received. The per-protocol population is used for sensitivity (secondary, supportive) analyses of efficacy endpoints.

Each of the patient populations listed above may be further subdivided for certain analyses (e.g., by age, race or gender) to assess whether certain subpopulations benefited from treatment with alvocidib more than others or if certain subgroups experienced greater toxicity from exposure to alvocidib.

